8.8.9.1. Columbia-Suicide Severity Rating Scale

As required in the US by the Food and Drug Administration (FDA), for clinical trials of CNSacting medications, changes in depression/suicidality as assessed by the C-SSRS will be monitored over the course of the trial to ensure patient safety.

The C-SSRS is a tool used not only to predict suicide attempts but to assess the full range of evidence-based ideation and behavior items, with criteria for next steps (e.g., referral to a MHP). There are 2 versions of the C-SSRS that will be administered:

• The **Screening** version of the scale documents recent (within the past month) scores from the screening C-SSRS scale. This version can assess a patient's eligibility based on inclusion/exclusion criteria.

[Note that patients will have completed the Baseline/Screening version of the C-SSRS scale during the index trial and are therefore not expected to complete this version in the current trial. **Thus, the baseline assessment that was collected at the beginning of the index trial should continue to be used as the baseline for this trial.** (The Baseline/Screening version of the scale combines the Baseline and Screening forms to assess suicidality in a patient's lifetime and during a predefined time period. This version can assess a patient's lifetime suicidality for data collection

purposes as well as eligibility, based on inclusion/exclusion criteria, for the index trial.)]

• The Since Last Visit version of the scale assesses suicidality since the patient's last visit. This version is meant to assess patients who have completed at least 1 initial C-SSRS assessment and should be used in every subsequent visit. The 'Since Last Visit' version of the C-SSRS is asking about any suicidal thoughts or behaviors the patient/participant may have had since the last time you have administered the C-SSRS.

To be eligible for the trial, a patient cannot have suicidal ideation of type 4 or 5, any lifetime history of suicide attempt, or any suicidal behavior in the last month in patients with no significant neurocognitive deficits.

Pediatric patients may not be able to complete the C-SSRS as intended. If in the clinical opinion of the Investigator a specific patient cannot complete the instrument, the following strategies may be employed:

- Site staff may administer the questions directly to the patient or may ask for the information from a third party, such as a caregiver or family members, as appropriate.
- The Investigator may use his/her clinical judgment to skip any questionnaires that he/she feels are not appropriate for a specific patient.

Any deviation from the intended use of an instrument should be documented by the Investigator, along with the reason for the deviation. If the C-SSRS is not administered, the Investigator should document that the issue of suicidality was assessed clinically (e.g., discussion with caregivers).

A patient should be referred to an MHP if he/she has:

- Any suicidal behavior.
- Any suicidal ideation of type 4 or 5 on the C-SSRS.

A referral to a MHP should also be made if, in the opinion of the Investigator, it is necessary for the safety of the patient. If a patient's psychiatric disorder can be adequately treated with psychoand/or pharmacotherapy, then the patient, at the discretion of the MHP, should be continued in the trial.

8.8.9.2. PHQ-9

The PHQ-9 is a 9-item depression scale of the Patient Health Questionnaire. The PHQ-9 is a tool for assisting clinicians in diagnosing depression as well as selecting and monitoring treatment. After the patient has completed the PHQ-9 questionnaire, it is scored by the trial staff.

8.8.10. Overdose

In the event of an overdose, the Investigator should contact the Medical Monitor immediately. Appropriate supportive treatment should be initiated according to the patient's clinical signs and symptoms.

The quantity of the excess dose and the duration of the overdose are to be documented in the eCRF.

Decisions regarding dose interruptions or modifications will be made by the Investigator in consultation with the Medical Monitor based on the clinical evaluation of the patient.

8.8.11. Adverse and Serious Adverse Events

AEs will be reported by the patient (or, when appropriate, by a caregiver, surrogate, or the patient's legally authorized representative).

The Investigator and any designees are responsible for detecting, documenting, and recording events that meet the definition of an AE or SAE and remain responsible for following up AEs that are serious, considered related to the study treatment or trial procedures, or that caused the patient to discontinue study treatment (see Section 6.4).

Details on recording AEs and SAEs, including definitions, are provided in Appendix 3.

8.8.11.1. Time Period and Frequency for Collecting AE and SAE Information

All AEs, including SAEs, will be collected from the start of the Run-in Period to the end-of-trial visit (Week 30). AEs reported after starting the Run-in Period will be considered treatment-emergent AEs.

Medical occurrences that begin before the start of the Run-in Period but after obtaining informed consent will be recorded on the Medical History/Current Medical Conditions section of the eCRF not the AE section.

All SAEs will be recorded and reported to the Sponsor or designee within 24 hours from the point in time when the Investigator becomes aware of the SAE. All SAEs must be reported whether or not considered causally related to the study drug. The Investigator will submit any updated SAE data to the Sponsor within 24 hours of it being available.

Investigators are not obligated to actively seek AEs or SAEs in former trial patients. However, if the Investigator learns of any SAE, including a death, at any time after a patient has been discharged from the trial, and he/she considers the event to be reasonably related to the trial treatment or trial participation, the Investigator must promptly notify the Sponsor.

The method of recording, evaluating, and assessing causality of AE and SAE and the procedures for completing and transmitting SAE reports are provided in Appendix 3.

8.8.11.2. Method of Detecting AEs and SAEs

Care will be taken not to introduce bias when detecting AEs and/or SAEs. Open-ended and nonleading verbal questioning of the patient is the preferred method to inquire about AE occurrences.

8.8.11.3. Follow-up of AEs and SAEs

After the initial AE/SAE report, the Investigator is required to proactively follow each patient at subsequent visits/contacts. All SAEs will be followed until resolution, stabilization, the event is otherwise explained, or the patient is lost to follow-up. Further information on follow-up procedures is given in Appendix 3.

8.8.11.4. Regulatory Reporting Requirements for SAEs

- Prompt notification by the Investigator to the Sponsor of a SAE is essential so that regulatory obligations and ethical responsibilities toward the safety of patients and the safety of a study treatment under clinical investigation are met.
- The Sponsor has a legal responsibility to notify both the local regulatory authority and other regulatory agencies about the safety of a study treatment under clinical investigation. The Sponsor will comply with country-specific regulatory requirements relating to safety reporting to the regulatory authority, IRBs, and investigators.
- Investigator safety reports must be prepared for suspected unexpected serious adverse reactions (SUSAR) according to local regulatory requirements and Sponsor policy and forwarded to Investigators, as necessary.
- An Investigator who receives an investigator safety report describing a SAE or other specific safety information (e.g., summary or listing of SAEs) from the Sponsor will review and then file it along with the Investigator's Brochure and will notify the IRB, if appropriate according to local requirements.

9. STATISTICS

This section describes the plans for analysis. Details of the statistical methodology for summaries and statistical analyses will be provided in a separate statistical analysis plan (SAP), which will be maintained by the Sponsor. The SAP may modify the plans outlined in the protocol; however, any major modifications of the primary endpoint definition and/or its analysis will also be reflected in a protocol amendment. If, after the trial has completed, changes are made to the SAP, then these deviations to the plan will be listed, along with an explanation as to why they occurred, in the clinical trial report for the trial, as appropriate.

9.1. Sample Size Determination

The primary objective is to assess steady-state PK parameters (maximum plasma concentration $[C_{max}]$, time to maximum plasma concentration $[T_{max}]$, trough plasma concentration $[C_{trough}]$, area under the plasma concentration-time curve over the dosing interval $[AUC_{0-tau}]$) for QW compared with QD setmelanotide. The sample size is based on availability of the patients enrolled in the LTE trial and is not driven by formal statistical hypothesis testing on non-inferiority/similarity.

9.2. **Populations for Analyses**

The analysis populations are defined as follows:

- Pharmacokinetic Analysis Set (PKAS): All patients who receive at least 1 dose of setmelanotide and who have a sufficient number of measurable plasma concentrations to permit assessment of noncompartmental parameters.
- Full Analysis Set (FAS): All patients who receive at least 1 dose of setmelanotide. Patients will be analyzed according to their randomly assigned treatment.

- Per Protocol Set: All patients in FAS without any major protocol violations that would result in exclusion of the patients from the analysis. Patients will be analyzed according to their randomly assigned treatment.
- Safety Analysis Set: All patients who are randomized and receive at least 1 dose of protocol-specified study drug. Patients will be analyzed according to the treatment they actually received.

9.3. Statistical Analyses

9.3.1. Primary Analysis of PK Parameters

The PK profile of the 2 formulations of setmelanotide will be characterized and the steady-state PK parameters (C_{max}, T_{max}, C_{trough}, and AUC_{0-tau}) will be summarized for QD and QW setmelanotide by dose level and prior treatment regimen (QW or QD) during the double-blind phase of the trial using descriptive statistics (e.g., n, mean, standard deviation, geometric mean, minimum, median, maximum, % coefficient of variation [CV], geometric mean CV, and confidence interval [CI]).

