- ¹⁴ Patients will undergo serial blood samples taken for measurement of steady-state setmelanotide concentrations (both QD and QW) and PK profiles will be performed. On the first day of the Run-in Period, blood samples for the QD PK profile will be drawn within 30 minutes prior to dose administration. Postdose samples will be collected at: 0.5, 1, 2 (±5 mins), 6, 8, 12, and 24 hours (±30 min). At minimum, mandatory postdose samples must be collected at: 6 and 8 hours (±30 min) and at 24 hours (±30 min). At Week 14, blood samples for the PK profiles will be drawn within 30 minutes prior to dose administration. Postdose samples will be collected at: 0.5, 1, 2 (±5 mins), 6, 8, 12, 24, 48, 72, 96, 120, and 168 hours (±30 min). At minimum, mandatory postdose samples must be collected at: 6 and 8 hours (±30 min), 24 hours (±30 min), 48, 72, 96, 120 hours (±30 min), and 168 hours (±30 min) In case of significant challenges with the collection of any PK sample, the investigator should confirm sample prioritization with the sponsor. Patients/caretakers will be reminded that there should be NO study drug administration at home on the day of clinic visits and that the predose (trough) blood draw must occur PRIOR to study drug administration. The blood draws for the Week 14 PK sampling must occur exactly 7 days after the prior visit. The Investigators will adhere to the site-specific blood volume limits for safety laboratory and PK analyses both to ensure minimal distress and reduce the number of venipunctures in pediatric patients. For patients <18 years of age, it may not be possible to collect all labs at every trial visit, though efforts should be made to collect as many PK samples per protocol. Venipuncture reduction is allowed should a patient <18 years of age experience unacceptable discomfort as deemed by the Investigator.

- ¹⁵ Injection site evaluations and scoring (by the clinical staff) will include identification of areas of erythema, edema, and induration, as well as the presence of localized pain, tenderness, and itching. At in-person trial visits, the clinical staff will also record measurements of areas of erythema, edema, and induration if possible. Unscheduled evaluations may also be recorded as warranted by clinical conditions.

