 Patients will undergo serial blood samples taken for measurement of steady-state setmelanotide concentrations (both QD and QW) and 24-hour PK profiles (including optional timepoint at 12 hours after dosing) will be performed. On the first day of the Run-in Period, blood samples for the QD PK profile will be drawn within 5 minutes prior to dose administration and at 0.5, 1, and 2 hours ( $\pm 5$  min) postdose and at 3, 4, 6, and 8 hours ( $\pm 10$  min) postdose. At Week 14, blood samples for the PK profiles will be drawn within 5 minutes prior to dose administration and at 0.5, 1, and 2 hours ( $\pm 5$  min) postdose and at 3, 4, 6, and 8 hours ( $\pm 10$  min) postdose and at 24 hours postdose. When possible, additional optional blood draws will be done at 48, 72, 96, 120, and 148 hours. Patients/caretakers will be reminded that there should be NO study drug administration at home on the day of clinic visits and that the predose (trough) blood draw must occur PRIOR to study drug administration. The blood draws for the Week 14 PK sampling must occur exactly 7 days after the prior visit.

 Injection site evaluations and scoring (by the clinical staff) will include identification of areas of erythema, edema, and induration, as well as the presence of localized pain, tenderness, and itching. At in-person study visits, the clinical staff will also record measurements of areas of erythema, edema, and induration if possible. Unscheduled evaluations may also be recorded as warranted by clinical conditions.

 Safety laboratory tests will include: complete blood count with platelet count and standard indices, chemistry panel, coagulation, and urinalysis with microscopic analysis (if positive findings on dipsticks warrant further examination).

 Any patient with a positive ADA at the end of study or early termination will be followed every 3 months after the sample analysis until resolution (ie, no measurable ADA response).

-  All BP and HR measurements are to be obtained in the sitting position following at least 5 minutes of rest. All measurements will be taken in triplicate, approximately 2 minutes apart. When possible, BP should be taken in the non-dominant arm throughout the study, using the same methodology (automated or manual). Body temperature (°C) and respiration rate (breaths/minute) will be obtained in the sitting position following at least 5 minutes of rest.

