##### **4.4.1. Primary [REDACTED] Analysis**

For the primary [REDACTED] endpoint, the PK profile of the 2 formulations of setmelanotide will be characterized and the steady-state PK parameters ( $C_{max}$ ,  $T_{max}$ ,  $C_{trough}$ ,  $AUC_{0-tau}$ ) will be summarized by dose level and prior treatment regimen (QW or QD) during the double-blind phase of the study using descriptive statistics including n, mean, standard deviation,

geometric mean, minimum, median, maximum, % coefficient of variation (CV), geometric mean CV, and 95% confidence intervals (CIs).

A separate tabulation will be created for the same analysis by subgroup (age category and genetic subgroup).

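### T_max is given the same geometric mean, CVs and untargeted 95% CI as the concentration parameters, and these statistics can fail for it

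*Protocol*

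**What the plan says.** Protocol 9.3.1 treats the four primary parameters as one group: "steady-state PK parameters (C_{max}, T_{max}, C_{trough}, and AUC_{0-tau}) will be summarized for QD and QW setmelanotide by dose level and prior treatment regimen". The statistics are offered as examples: "using descriptive statistics (e.g., n, mean, standard deviation, geometric mean, minimum, median, maximum, % coefficient of variation [CV], geometric mean CV, and confidence interval". No CI level is given.

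SAP 4.4.1 repeats the grouping, replaces the examples with a list that is to be included, and sets the level: "geometric mean, minimum, median, maximum, % coefficient of variation (CV), geometric mean CV, and 95% confidence intervals (CIs". It repeats the analysis by age category and genetic subgroup. SAP 3.2 promises CIs on selected parameters as described later, but 4.4.1 makes no selection. Neither document says whether the CI is for the arithmetic mean, the geometric mean or the median. No visible passage gives T_max its own rule.

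The sampling times are in footnote 14 of the schedule in each document. For Week 14 the protocol has a predose sample and then: "Postdose samples will be collected at: 0.5, 1, 2 (±5 mins), 6, 8, 12, 24, 48, 72, 96, 120, and 168 hours". For the run-in: "Postdose samples will be collected at: 0.5, 1, 2 (±5 mins), 6, 8, 12, and 24 hours", with a reduced minimum: "mandatory postdose samples must be collected at: 6 and 8 hours (±30 min) and at 24 hours". The SAP footnote differs. It adds 3 and 4 h samples and makes the late ones optional: "When possible, additional optional blood draws will be done at 48, 72, 96, 120, and 148 hours".

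**The concern.** A log-scale summary suits C_max, C_trough and AUC, which are positive and roughly continuous. T_max is the time of the highest observed sample, so its values bunch around the scheduled times. On the protocol's Week 14 schedule the gaps run from 2 to 6 h, from 12 to 24 h, then daily, then 48 h. Time zero is a possible value, because the predose sample belongs to the profile. SAP 1.1.1 describes the weekly product as a depot that releases drug slowly, so a flat steady-state profile with its highest sample at predose cannot be ruled out.

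T_max is part of the primary endpoint, and with no hypothesis tests planned these summaries are the primary analysis. At stake is a primary table that could show an impossible interval, a geometric mean of zero, or a geometric mean from which a patient has been dropped without comment.

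**Working it through.** The documents give no T_max distribution, variance or precision target, so there is no planned figure to reproduce. The only benchmark is the SAP's nominal 95%.

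**Inputs.** About 30 patients randomized 1:1 gives about 15 per arm. Spread evenly over three dose levels, that is 15/3 = 5 per cell. The even spread is an assumption, because randomization is stratified by age only and the dose mix is not stated. About 4 patients are aged 6 to under 12, or about 2 per arm.

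**Geometric statistics with a zero.** The geometric mean is the exponential of the mean log value. One T_max of 0 makes the product zero and the log undefined. Using actual clock times does not help, because a predose draw is then at or just before time zero. If a proportion p of patients peak at predose (assumption), the chance of at least one in a cell is 1 − (1 − p)^n:

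| p | n = 5 | n = 15 |
|---|---|---|
| 5% | 23% | 54% |
| 10% | 41% | 79% |
| 20% | 67% | 96% |

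**Arithmetic-mean t interval.** The lower limit is mean − t × SD/√n. It is negative exactly when the sample CV exceeds √n / t(0.975, n−1). This needs no distributional assumption.

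| n | t | CV threshold |
|---|---|---|
| 2 | 12.706 | 0.11 |
| 3 | 4.303 | 0.40 |
| 5 | 2.776 | 0.81 |
| 8 | 2.365 | 1.20 |
| 15 | 2.145 | 1.81 |

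Example at n=5 with protocol sampling times 2, 2, 6, 8 and 24 h: mean 42/5 = 8.4 h, SD 9.10 h, CV 1.08. The half-width is 2.776 × 9.10/√5 = 11.3 h, so the CI is −2.9 to 19.7 h. A log-scale CI for the geometric mean is 1.5 to 19.8 h, and the median is 6 h.

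Example at n=2 with 6 and 8 h: mean 7 h, SE 1 h, CI 7 ± 12.7, or −5.7 to 19.7 h. If all values tie, the SD is 0 and either type of CI has zero width.

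**Coverage under assumed distributions.** Log-normal T_max was moved to the nearest protocol sampling time, with median 2 to 8 h for QD and 4 to 48 h for QW, and CV 30% to 150%. The nominal 95% t interval for the mean covered 61% to 95% at n=5 and 81% to 97% at n=15. Its lower limit was negative in 0% to 63% of samples at n=5 and 0% to 7% at n=15. A narrower set of assumptions (median 8, 24 or 48 h, CV 50% to 150%) gave 77% to 91% coverage at n=5. With no sampling grid at all, skewness alone gave 80% to 94% at n=5. The log-scale CI stayed above zero and covered 61% to 96% at n=5, failing mainly when most patients shared one time.

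**The range already planned.** Minimum to maximum covers the population median with probability 1 − 2 × 0.5^n: 75% at n=3, 93.75% at n=5 and 96.9% at n=6. It cannot be negative if a predose peak is recorded as 0 h.

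**The case against.** The strongest reply is that this is a small matter of presentation. Median, minimum and maximum are in both lists. SAP 3.2 and 3.7 make the study descriptive, and no test, margin or conclusion rule uses the T_max interval. The protocol's list is only illustrative. Parts of the SAP's section on PK parameters are not in the public text, so a separate rule for T_max may exist there. All of this stands, and it limits the weight of the point.

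A reader might infer that T_max can take only the nominal times. The documents do not support that: Protocol 8.6 requires actual clock times, and neither document says which times define T_max. With windows of ±5 or ±30 minutes on the protocol schedule, the values still cluster.

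A reader might also infer that the planned interval is mean-based and will go negative. That too goes beyond the text, since the CI's target is not named and a log-scale interval cannot fall below zero. But that interval cannot be computed when a T_max is 0, so neither reading is safe.

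Finally, the coverage loss is not established and should not be put down to the sampling grid alone. The distributions and dose-cell sizes are assumed, skewness contributes, and some scenarios reach nominal coverage. If most patients are on one dose, that cell approaches 15 per arm, where negative limits are uncommon. The SAP's 3 and 4 h samples would also close the 2 to 6 h gap.

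**Conclusion.** The point holds in a limited form. As written, the SAP prescribes for T_max statistics that are zero or undefined after a single predose peak, together with a 95% CI whose target is unspecified. If that target is the arithmetic mean, the CV thresholds for a negative lower limit are exact and are easily reached in cells of 2 to 5 patients. How often this would happen, how often a T_max of 0 would occur, and how far coverage would fall short all rest on assumptions that the documents neither supply nor contradict. A flat claim that the interval under-covers is not supported; that it may do so in small dose-level or age cells is. The consequence is an uninterpretable line in a primary table and not a wrong trial decision. It is worth correcting because T_max is a named component of the primary endpoint.

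**What to change.** In SAP 4.4.1, with Protocol 9.3.1 aligned:

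- Summarize T_max by n, median, minimum and maximum, optionally with quartiles or counts by sampling time.
- Drop the geometric mean, both CVs, and any mean-based or log-scale CI for T_max.
- State that the 95% CIs for C_max, C_trough and AUC_0-tau are for the geometric mean, computed on the log scale and back-transformed.
- Say whether T_max uses nominal or actual times, and how a predose peak is recorded.

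An exact interval for the median, or a Hodges-Lehmann interval for a QW–QD difference, could be added but is not needed. The cost is a few lines of SAP wording and one table shell, with no new data. The only loss is that small cells show a range and no 95% interval for T_max; at n=5 even the full range gives 93.75% for the median.
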